**LIST OF ABBREVIATIONS**

AE	Adverse Event
ALT	Alanine Aminotransferase
ALC	Absolute Lymphocyte count
ASCO	American Society of Clinical Oncology
AST	Aspartate Aminotransferase
BUN	Blood Urea Nitrogen
CBC	Complete Blood Count
CMP	Comprehensive Metabolic Panel
CR	Complete Response
CT	Computed Tomography
CTCAE	Common Terminology Criteria for Adverse Events
DLT	Dose Limiting Toxicity
DOT	Disease Oriented Team
DSMC	Data and Safety Monitoring Committee
ECOG	Eastern Cooperative Oncology Group
FDA	Food and Drug Administration
GCP	Good Clinical Practice
H&P	History & Physical Exam
HRPP	Human Research Protections Program
IHC	Immunohistochemistry
IND	Investigational New Drug
IV (or iv)	Intravenously
MRI	Magnetic Resonance Imaging
MTD	Maximum Tolerated Dose
NCI	National Cancer Institute

ORR	Overall Response Rate
OS	Overall Survival
PBMCs	Peripheral Blood Mononuclear Cells
pCR	Pathologic Complete Response
PD	Progressive Disease
PET	Positron Emission Tomography
PFS	Progression Free Survival
p.o.	peros/by mouth/orally
PR	Partial Response
RCB	Residual Cancer Burden
RECIST	Response Evaluation Criteria in Solid Tumors
SAE	Serious Adverse Event
SCCC	Simmons Comprehensive Cancer Center
SD	Stable Disease
SGOT	Serum Glutamic Oxaloacetic Transaminase
SGPT	Serum Glutamic Pyruvic Transaminase
WBC	White Blood Cells

## STUDY SCHEMA

The schema should represent your study design, along with corresponding descriptive text, as applicable.

**STUDY SUMMARY**

Title	Initial evaluation of role of early interim F-FLT PET/CT for outcome prediction in pancreatic adenocarcinoma
Short Title	FLT PET/CT and Pancreatic cancer early therapy assessment
Protocol Number	Version 7
Phase	Clinical study phase (e.g., Phase II)
Methodology	Prospective cohort study
Study Duration	2 years
Study Center(s)	UT Southwestern Medical Center - Single-center
Objectives	
 
• To assess if percentage change in F-FLT PET/CT quantitative parameters (SUV max, or SUV peak or proliferative tumor volume) after 2 cycles of neoadjuvant chemotherapy can predict overall survival at 1 and 2 years and progression free survival at 6 months and 1 year in patients with resectable, borderline resectable or locally advanced pancreatic adenocarcinoma.
 

Number of Subjects	20 patients with pancreatic adenocarcinoma

Diagnosis and Main Inclusion and exclusion Criteria	
 
• Patients must be over 18 years old and capable and willing to provide informed consent
 
• Patients of childbearing potential must have a negative urine or serum pregnancy test within 7 days prior to PET/CT imaging per institution's standard of care
 
• Medically stable as judged by patient's physician
 
• Patients must have an ECOG performance status of 0-3 (restricted to ECOG PS 0-2 if age >70 years)
 
• Patients with known allergic or hypersensitivity reactions to previously administered radiopharmaceuticals of similar chemical or biologic composition to FLT are not eligible
 
• Patient must NOT be breast-feeding
 
• Histologically confirmed resectable, borderline resectable or locally advanced pancreatic adenocarcinoma 
 
• Patient have measurable disease (by RECIST 1.1 criteria)
 
 
 
• Patients with a history of prior therapy for pancreatic adenocarcinoma are NOT eligible 
 
• Patient must not weigh more than the maximum weight limit for the table for the PET/CT scanner (>200kg or 440lbs).
 
 
 
• Patient must be able to lie still for a 20 to 30 minutes for whole body PET/CT scan
 

Study Product(s), Dose, Route, Regimen	Fluorothymidine is an analog of the nucleoside thymidine (deoxythymidine) but the 3'-F atom prevents FLT from following the full biochemical pathway of thymidine. FLT is transported from the blood into cells by active transport; it does not freely diffuse across the cell membrane. Once in the cell, FLT is a substrate for thymidine kinase I (TK1) and is phosphorylated but is not incorporated into DNA. 5mCi of FLT (+/- 20%) will be given intravenously.
Duration of administration	IV push over one to two minutes
Reference therapy	Not applicable

Statistical Methodology	
The difference in SUVmax, SUVpeak and proliferative tumor volume between baseline and post 2 cycles of chemotherapy will be correlated with overall survival at 1 and 2 years (primary clinical outcome endpoint) and progression free survival at 6 months and at 1 year (secondary clinical outcome endpoint) of patients with resectable, borderline resectable or locally advanced pancreatic adenocarcinoma using univariate and multiple cox regression model. Patient demographic information and tumor and treatment characteristics such as sex, race, tumor grade, cancer stage, last treatment modality, will also be included. P value less than 0.05 will be considered as statistical significant.
 
Areas under the ROC curve (AUC) and corresponding 95% confidence interval will be calculated for all models. Leave one out cross validation will be applied to avoid over-fit.

-------------------------	---

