## **2.0 STUDY OBJECTIVES**

### **2.1 Primary Objectives**

- a. To assess if percentage change in FFLT PET/CT quantitative parameters (SUV max, or SUV peak or proliferative tumor volume) after 2 cycles of chemotherapy can predict overall survival at 1 and 2 years in patients with resectable, borderline resectable or locally advanced pancreatic adenocarcinoma.

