### **3.2 Exclusion Criteria**

- a. Subjects who had prior chemotherapy or radiotherapy for pancreatic adenocarcinoma cannot participate in the study.
- b. Patient must NOT be pregnant or breast-feeding.
- c. Patients have no clinical evidence of distant metastatic disease
- d. Patients must not weigh more than the maximum weight limit for the table for the PET/CT scanner where the study is being performed.(>200kg or 440lbs)

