#### 6.4.3 Evaluation of Best Overall Response

The best overall response is the best response recorded from the start of the treatment until disease progression/recurrence (taking as reference for progressive disease the smallest measurements recorded since the treatment started). The subjects best response assignment will depend on the achievement of both measurement and confirmation criteria.

Target Lesions	Non-Target Lesions	New Lesions	Overall Response	Best Response for this Category Also Requires:
CR	CR	No	CR	$\geq 4$ wks. confirmation
CR	Non-CR/Non-PD	No	PR	$\geq 4$ wks. confirmation
PR	Non-PD	No	PR	
SD	Non-PD	No	SD	Documented at least once $\geq 4$ wks. from baseline
PD	Any	Yes or No	PD	No prior SD, PR or CR
Any	PD*	Yes or No	PD	
Any	Any	Yes	PD	

\* In exceptional circumstances, unequivocal progression in non-target lesions may be accepted as disease progression.

Note: Subjects with a global deterioration of health status requiring discontinuation of treatment without objective evidence of disease progression at that time should be reported as “*symptomatic deterioration*”. Every effort should be made to document the objective progression even after discontinuation of treatment.

Note: If subjects respond to treatment and are able to have their disease resected, the patient’s response will be assessed prior to the surgery.

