## **9.2 Sample size**

The sample size was based on an ability to detect a relative group difference in FLT SUV (baseline versus interim) of 0.124 and standard deviation of 0.17. A sample size of 15 patients was calculated using a two-sided paired t test, power of 80 %, and the type I error rate was set to be 0.05. The expected response to therapy was assumed to be 20%.

Five patients were added to the sample size to compensate for dropout and no uptake on the baseline scan, leading to a total sample size of 20.

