## **9.3 Data Analyses Plans**

Primary outcome variable: The difference in SUVmax, SUVpeak and proliferative tumor volume between baseline and 2 cycles of chemotherapy will be correlated with overall survival at 1 and 2 years and with progression free survival at 6 months and at 1 year.

The primary outcome of the study is to establish which degree of change in the PET/CT quantitative parameters can predict patients overall survival and progression free survival. The SUVmax (representing the single voxel with the highest activity concentration), SUV peak (which is defined as the average SUV within a 1 cubic cm volume within the region of the tumor with the highest metabolic activity) and proliferative tumor volume of the pancreatic tumor will be measured.

Univariate and multiple cox regression model are going to be used. P-value less than 0.05 will be considered as statistical significant.

Secondary outcome variable: the difference in SUVmax, SUVpeak and proliferative tumor volume between baseline and 2 cycles of chemotherapy will be correlated with binary tumor outcome measured from MRI/CT (resectable versus non-resectable disease) at 6 month using logistic regression. A multiple logistic regression with stepwise selection algorithm will be used to select the most correlated variable(s). Areas under the ROC curve (AUC) and corresponding 95% confidence interval will be calculated for all models. Leave one out cross validation will be applied to avoid over-fit.

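### The Study Summary adds an open list of clinical covariates to the Cox analysis that section 9.3 does not mention; if five enter together on at most 20 deaths, the nominal 5% test of a PET term runs at about 11–13%

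*Combined protocol and SAP*

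**What the plan says.** The Statistical Methodology entry of the Study Summary correlates the changes in SUVmax, SUVpeak and proliferative tumor volume with overall survival and progression-free survival by univariate and multiple Cox regression. The next sentence reads: "Patient demographic information and tumor and treatment characteristics such as sex, race, tumor grade, cancer stage, last treatment modality, will also be included". The significance threshold is 0.05. The entry then turns to ROC areas for all models and adds: "Leave one out cross validation will be applied to avoid over-fit".

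Section 9.3 states the same Cox plan at the same threshold: "Univariate and multiple cox regression model are going to be used". It names no clinical covariate. Its only variable-selection rule, a stepwise algorithm, belongs to the secondary logistic model for resectability at 6 months, and its leave-one-out sentence stands in that same paragraph.

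Section 2.1 joins the PET parameters with *or*: "SUV max, or SUV peak or proliferative tumor volume) after 2 cycles of chemotherapy". Section 9.3 lists all three. It is therefore open whether a Cox model carries one PET change or three.

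Section 9.2 fixes enrolment, "leading to a total sample size of 20", of which 15 is the calculated number and five cover dropout and absent baseline uptake. On earlier treatment, section 3.2 says: "Subjects who had prior chemotherapy or radiotherapy for pancreatic adenocarcinoma cannot participate in the study".

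**The concern.** Two analysts working from this document could fit different Cox models to the primary question. One would adjust for sex, race, grade, stage and last treatment modality, and perhaps for more, since the list is open. The other, reading section 9.3 alone, would see no clinical covariate to include. The plan does not say which Cox result decides whether PET change predicts survival.

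The choice affects the error rate. With at most 20 deaths, a model with six or more covariates is too large for the usual Wald and LR approximations, and a P value below 0.05 then occurs by chance more often than 5% of the time.

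Last treatment modality raises a further problem. It is undefined, and because prior therapy is excluded it can vary only after entry. Unless it is restricted to what is known at the interim scan, the model could condition on something that happened after the PET change was measured.

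**Working it through.** **1. The plan's own figure.** Section 9.2 uses a difference of 0.124, SD 0.17, two-sided 0.05 and 80% power in a paired t test. The normal approximation gives ((1.960 + 0.842) × 0.17 / 0.124)² = (2.802 × 1.371)² ≈ 14.8, rounded up to 15, so the stated number reproduces. (The exact t calculation needs 17; power at 15 is 74.8%.) Adding five gives 20. Deaths, the Cox model and the number of covariates play no part in this calculation.

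**2. Events per covariate.** Five clinical covariates plus one PET change make 6; with three PET changes, 8. If all 20 patients die, the ratio is 20/6 = 3.3 or 20/8 = 2.5. With 15 evaluable patients, all dying, it is 15/6 = 2.5 or 15/8 = 1.9.

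**3. Null rejection rates.** PET changes and covariates were simulated unrelated to survival, and one PET term was tested at nominal 5% by LR and Wald. The documents state neither the coding nor the test, so these are assumptions: binary clinical covariates entered jointly, and both tests shown. Every patient dying needs no assumption about survival. Runs typically used 2,000 to 6,000 datasets per setting (Monte Carlo error about 0.3 to 1 percentage point); ranges span the runs.

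| Cox model | n = 20, LR / Wald | n = 15, LR / Wald |
|---|---|---|
| One PET change alone | near 5–7%, either test | near 5–7%, either test |
| Three PET changes only | about 8% / 7% | 9–10% / 8% |
| One PET + five clinical | 12–13% / 11–12% | about 16% / 13% |
| Three PET + five clinical | 16–17% / 14–15% | 21–25% / 17–20% |

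**4. More factor levels.** Eligibility admits three stage categories. With stage at three levels (six clinical terms), one PET change, n = 20 and all dying, the rate is 13.8% by LR and 12.1% by Wald. At nine clinical terms it is 20.2% and 18.2%; at eleven, 26.1% and 23.0%.

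**5. Fewer deaths.** The documents give no expected number of deaths. Assume exponential survival with median 15 to 20 months, and follow-up of 24 months (section 4.0) or 30 months (6 months to end of treatment, section 9.1, plus 2 years, section 4.1). Expected deaths are n × (1 − 2^(−follow-up/median)): from 15 × (1 − 2^(−24/20)) = 8.5 to 20 × (1 − 2^(−30/15)) = 15.0. With 6 or 8 covariates the rates are 12–23% by LR and 8–15% by Wald. Divergent fits become common: up to 11% at n = 20; at n = 15, 3–25% with 6 covariates and 12–39% with 8.

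**6. Other entry rules.** If covariates were first screened univariably (P < 0.05 or P < 0.20 assumed; the plan states no such rule), the rate is 6–7.5% by LR and 5–6.4% by Wald. One PET change plus one covariate gives 6–8.5% by LR and 5–7% by Wald.

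**7. Leave-one-out.** It yields held-out predictions, here for the ROC areas. The Cox P values come from the full data and do not change.

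**The case against.** The strongest reply is that the plan never says the covariates enter together. The Summary's sentence also fits one-at-a-time models, or univariable screening before a multiple model, and step 6 shows that screening removes most of the inflation. This stands: the figures are conditional on joint entry. The point survives because the multiple Cox regression followed by a statement that these items will be included makes joint entry the natural reading, and because the error rate should not hang on an unstated rule.

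Section 9.3 does not exclude clinical covariates. It too specifies a multiple Cox model and is simply silent on them. A reader might infer a flat contradiction; the texts show an omission that needs reconciling.

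A reader might also infer that the five clinical covariates by themselves take the error rate to about 24% on 20 deaths. They do not. With binary coding, rates of that size need 15 patients, all three PET changes in the model and the LR test; three PET terms alone already give about 8–10% by LR. At 20 patients such rates need a much richer coding, which the plan does not specify.

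On last treatment modality, it is tempting to conclude that adjustment would remove the very response PET should predict, since section 6.4.3 says: "If subjects respond to treatment and are able to have their disease resected". That note concerns when response is assessed before surgery and does not define the covariate. Section 9.1 mentions chemotherapy alone or chemoradiation, a plausible meaning of the term. What stands is that the item is undefined and arises after entry.

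Finally, the title calls this an initial evaluation, which lessens the weight of strict error control. The plan nevertheless applies a 0.05 threshold to its primary question.

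**Conclusion.** The point holds as a gap in specification with a measurable consequence. The Summary and section 9.3 must be reconciled, and the plan must say which Cox result is primary. Under joint entry of five binary covariates with one PET change and every patient dying, the nominal 5% test rejects a true null more than twice as often as stated at 20 patients: about 12–13% by LR (12/5 = 2.4 to 13/5 = 2.6 times) and 11–12% by Wald. At 15 patients it is about 16% and 13%. Adding all three PET changes gives about 16–17% and 14–15% at 20 patients, and 21–25% and 17–20% at 15, part of it due to the PET terms.

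These sizes rest on joint entry, the coding and the test, none of which the plan fixes. Additional factor levels raise them. Fewer deaths do not raise them uniformly: the Wald rate can fall to 8%, but more fits diverge, especially at 15 patients, so the lower rate does not show a sound analysis. The wording gap is certain; the percentages are conditional.

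**What to change.** - Make the Study Summary and section 9.3 agree on the Cox analysis.
- Name the univariable Cox model for one prespecified PET change as the primary analysis.
- Limit any adjusted Cox model to that change plus one prespecified baseline covariate with stated coding (for example stage), labelled as a sensitivity analysis.
- Remove last treatment modality from the model, or define it and restrict it to what is known by the interim scan.
- As a separate, minor clarification for the secondary logistic model, state that stepwise selection is repeated within each leave-one-out fold. The plan does not say either way.

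The cost is wording in the analysis plan; no new data are needed. Fewer adjusted estimates will be reported, and the one-covariate model still runs at about 6–8.5% by LR (5–7% by Wald), which is why it should be a sensitivity analysis. If the sponsor wants more adjustment, penalised Cox regression or permutation P values are alternatives to prespecify; neither was evaluated here.

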## 1.0 BACKGROUND AND RATIONALE

### 1.1 Disease Background

Pancreatic cancer is the fourth most lethal malignancy overall, with a projected death toll of more than 40,000 for 2016 in the US. Pancreatic adenocarcinoma is usually locally advanced and / or metastatic at the time of diagnosis, preventing surgical resection in the majority of cases. Initial treatment strategies for resectable, borderline resectable or locally advanced pancreatic adenocarcinoma includes chemotherapy and chemoradiation (in selected patients). The main therapeutic goal is to reduce disease burden to allow surgical resection, which is the only curative treatment for pancreatic adenocarcinoma to date. After initial treatment, response is reevaluated by anatomical imaging, usually by a dedicated contrast enhanced CT, which is preferred, or alternatively MRI. However, objective evaluation of response in pancreatic cancer is often difficult. CT and MRI have some significant limitations, such as inability to clearly outline tumor borders due to the infiltrative nature of pancreatic adenocarcinomas, and post-treatment imaging changes that can simulate tumor. Additionally, it is an anatomic method only that relies on relatively slow macroscopic tumor changes without information regarding tumor metabolism.

2-Deoxy-2-[F]-fluoro-D-glucose (F-FDG) PET/CT, which is a marker of glucose metabolism, is an alternative imaging method, and multiple studies have shown an overall sensitivity of 73 to 94% for detection of pancreatic adenocarcinoma, while specificity ranges from 60 to 89%. The specificity is reduced because F-FDG PET/CT is a non-specific tracer that also accumulates in some benign conditions with increased glucose metabolism (such as inflammation). Moreover, the rate of false negatives is also

increased in this population because 20 to 30% of patients with pancreatic adenocarcinoma have hyperglycemia, which may significantly decrease the amount of FDG uptake. For these reasons, more accurate novel PET tracers are expected to have a significant clinical impact.

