### 3.1 Inclusion Criteria

[figure not shown]
- a. Patients with histologically confirmed pancreatic adenocarcinoma (resectable, borderline resectable or locally advanced disease at presentation) are eligible for the study.
- b. Patients should not have any type of curative or palliative therapy for pancreatic adenocarcinoma before enrolling in the study and should be candidates for induction chemotherapy.
- c. Patients must be over 18 years old and capable and willing to provide informed consent.
- d. Patients must have measurable disease (by RECIST 1.1 criteria)
- e. Patients must have an ECOG performance status of 0-3 (restricted to ECOG PS 0-2 if age >70 years).
- f. Patients of childbearing potential must have a negative urine or serum pregnancy test within 7 days prior to the FLT PET/CT and the optional FDG PET/CT imaging per institution's standard of care; A female of childbearing potential is any woman (regardless of sexual orientation, having undergone a tubal ligation, or remaining celibate by choice) who meets the following criteria;
  - i. Has not undergone a hysterectomy or bilateral oophorectomy; or
  - ii. Has not been naturally postmenopausal for at least 12 consecutive months (i.e., has had menses at any time in the preceding 12 consecutive months).
- g. Medically stable as judged by patient's physician.

- h. Patients with known allergic or hypersensitivity reactions to previously administered radiopharmaceuticals of similar chemical or biologic composition to FLT or FDG are NOT eligible.
- i. Ability to understand and the willingness to sign a written informed consent.
- j. Patient must be able to lie still for a 20 to 30 minute PET/CT scan.

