**Visit 3:** Day of F-FLT-PET/CT: The patient will have an intravenous line placed in the hand or arm, F-FLT-PET/CT will be given by 1-2 minute IV push, and the dose administered will be approximately 5 mCi (+/- 20% dose). After approximately 60 +/- 10 minutes of uptake time, the patient will be positioned supine in the PET/CT scanner for standard whole body PET/CT scan from the skull base to mid-thigh. This scan will take approximately 20-30 min. The window from FLT PET/CT baseline study to initiation of chemotherapy should be no more than 30 days.

**Visit 4:** Day of Interim F-FLT-PET/CT: The interim F FLT-PET/CT will be performed after the 2nd cycle of chemotherapy regimen, but before the commencement of 3rd cycle. The second F-FLT-PET/CT study must be performed on the same scanner as the first F FLT-PET/CT and the imaging protocol described in Visit 3 should be closely followed.

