## **9.0 STATISTICAL CONSIDERATIONS**

### **9.1 Study Design/Study Endpoints**

We anticipate to enroll 20 patients with biopsy proven pancreatic adenocarcinoma that are not eligible for resection by the time of the diagnosis. These patients are going to be treated with chemotherapy only or chemoradiation in selected cases. These patients will undergo an optional F FDG PET/CT (as standard of care clinical baseline) and F-FLT PET/CT before treatment (research baseline study), and after two cycles of chemotherapy (research early therapy assessment study).

For the F-FLT PET/CT analysis, SUV max, SUV peak and proliferative tumor volume will be measured by MIMvista software and compared between the two studies. Tumor size and extension will also be evaluated on CT images from the PET/CT study.

At completion of treatment (6 months after baseline FLT PET/CT) an anatomic study (MRI or CT) will be performed as standard of care in our institution to reassess the tumor and classify it as resectable or non-resectable. Also at 6 months, 1 year and 2 years after initial baseline scan, or before if clinically indicated, standard of care anatomic study (MRI or CT) will also be performed and will be reevaluated by RECIST criteria to determine stability versus progression of disease.

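### Last treatment modality is listed as a Cox covariate with no definition or time cut-off; in its only informative reading it uses post-scan, survival-dependent information and can distort the adjusted FLT hazard ratio

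*Combined protocol and SAP*

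**What the plan says.** The covariate list appears only in the Study Summary, Statistical Methodology row, directly after the univariate and multiple Cox models of OS (primary) and PFS (secondary): "Patient demographic information and tumor and treatment characteristics such as sex, race, tumor grade, cancer stage, last treatment modality, will also be included". Section 9.3 repeats the method ("Univariate and multiple cox regression model are going to be used") but lists no covariates. No section defines the last-treatment-modality variable, sets a date at which it is read, makes it time-dependent, or starts the analysis from a landmark.

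Four other places bear on what the variable can mean:

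- Section 3.1(b), before entry: "Patients should not have any type of curative or palliative therapy for pancreatic adenocarcinoma before enrolling in the study". The same criterion says that patients "should be candidates for induction chemotherapy".
- Section 4.0, Visit 4, places the interim scan after the second "cycle of chemotherapy regimen, but before the commencement of" the third.
- Section 9.1, on treatment: "These patients are going to be treated with chemotherapy only or chemoradiation in selected cases".
- Section 1.1, on what follows: "The main therapeutic goal is to reduce disease burden to allow surgical resection". Section 9.1 places the reassessment of resectability 6 months after the baseline FLT scan.

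**The concern.** The primary objective asks whether FLT change, measured after two cycles, predicts survival. A covariate in that model should be known when the scan is read. A modality recorded later is not, and it causes two separate problems.

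First, a patient must be alive to start chemoradiation or to reach surgery. If the later modality is coded as though known from time zero, the months before it started count as survival under that modality. The modality then looks protective even if it does nothing.

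Second, receipt depends on survival and possibly on FLT change. Section 9.3 itself plans to test whether FLT change is related to resectability at 6 months. If it is, patients with a good FLT change who did not receive the later modality include a disproportionate number who died too early to get it. Conditioning on receipt then makes a good FLT change look worse than it is. If the modality also works, adjustment further removes the part of the prediction that runs through it.

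For PFS, a modality started after progression would be a covariate measured after the outcome. None of this depends on how many other covariates are in the model.

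**Working it through.** **No plan figure to reproduce.** The documents give no hazard ratio and no figure for this covariate. The sample size in 9.2 rests on a paired t test: (0.17 × (1.960 + 0.842) / 0.124)² = 14.75, rounded up to the stated 15. It does not bear on this point.

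**Step 1: what the variable can be at each time.**

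| Time | Last modality | Source |
|---|---|---|
| Entry | None | 3.1(b), 3.2(a) |
| Interim scan | Chemotherapy, essentially everyone | 3.1(b), 4.0 Visit 4 |
| After the scan | Chemotherapy, chemoradiation or resection | 9.1, 1.1 |

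Read at the scan it is nearly constant and useless. It varies usefully only if read afterwards, inside the OS and PFS follow-up.

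**Step 2: immortal time.** Assume exponential survival from the scan with median M of 12 or 18 months, and a later modality starting 2 to 7 months after the scan (midpoint 4.5). The share alive at the midpoint is 2^(−4.5/M):

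- M = 12: 2^(−0.375) = 0.77, so about 23% die before they could receive it.
- M = 18: 2^(−0.25) = 0.84, so about 16% do.

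All these early deaths fall in the group without the modality.

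**Step 3: effect on the FLT hazard ratio, by simulation.** All inputs are assumptions; none comes from the documents.

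- x = FLT reduction in SD units; hazard = (ln 2 / M) × exp(x × ln HR_direct), with M = 12 or 18 months.
- Log-odds of being selected for the later modality rise by 1 per SD of x (the link), or by 0 (no link).
- Start is 2 to 7 months after the scan, and the modality is received only if the patient is alive then; about half receive it. Censoring is at 22 months.
- After the start, the hazard is multiplied by the modality HR: 1 (inert) or 0.5.
- Two Cox models are fitted: x alone, and x plus a fixed indicator of receipt.

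| Direct FLT HR | Modality HR | Link | FLT HR, x alone | FLT HR, with modality |
|---|---|---|---|---|
| 1.0 | 1 | yes | 1.0 | about 1.13-1.15 |
| 0.60 | 1 | yes | 0.60 | about 0.70 |
| 0.60 | 0.5 | yes | 0.54-0.56 | 0.69-0.70 |
| 0.8 | 0.5 | yes | about 0.72 | about 0.94 |
| any of these | 1 or 0.5 | no | unchanged | unchanged |

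The inert modality shows an estimated HR of about 0.5.

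The share of the log hazard ratio that remains after adjustment varies widely:

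- Row 2: ln 0.70 / ln 0.60 = 0.357 / 0.511 = 70%.
- Row 3, at mid-range: ln 0.695 / ln 0.55 = 0.364 / 0.598 = 61%.
- Row 4: ln 0.94 / ln 0.72 = 0.062 / 0.329 = 19%.

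**Step 4: sensitivity to the assumptions.** A second set used medians of 10 and 16 months, censoring at 24 months, start at 2 to 6 months, and optional unmeasured prognosis (SD 0.7 on the log hazard).

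- Inert modality, no true FLT effect, link present: FLT HR 1.00-1.01 becomes 1.11-1.19; modality HR 0.38-0.58.
- Inert modality, direct FLT HR 0.60, link present: 0.60 becomes 0.66-0.67; with unmeasured prognosis, 0.65-0.66 becomes 0.76-0.77.
- No link: FLT HR nearly unchanged (for example 0.61 to 0.60), but an inert modality still shows 0.41-0.64.

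At n = 15 (median 16 months, no unmeasured prognosis), with no true FLT effect and an inert modality, rejection for FLT rises from 4.9% to 7.4% with the link and from 4.5% to 6.2% without it. Part of the rise is therefore small-sample inflation.

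**The case against.** The strongest reply is that the post-scan reading is an inference. The term is undefined, appears once, and sits in an illustrative list in a summary table, while Section 9.3 names no covariates. Read at the scan it would be nearly constant and harmless. This stands as a limit on certainty. It does not rescue the text: a covariate that is either uninformative or drawn from the future should not be listed without a cut-off.

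A reader might also infer that the primary analysis as a whole is invalid, or that the FLT hazard ratio must be biased. The documents support neither. Univariate FLT models are planned as well and are unaffected, and neither the Study Summary nor 9.3 makes the multiple model primary. In the multiple model the FLT estimate moves materially only if FLT change is related to later modality. The resectability analysis in 9.3 tests such a relation; it is not established.

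Finally, a reader might infer that adjustment wipes out most of the predictive signal. That happens in the scenario with a weak direct effect (0.8) and an effective modality, where 19% of the log hazard ratio is left. With a direct effect of 0.60, about 60% to 70% is left. The spurious HR of about 0.5 belongs to the modality coefficient, which no objective tests.

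**Conclusion.** The point holds and should be fixed before analysis. Following the Study Summary as written, the multiple Cox models would contain either a near-constant term or a fixed covariate that uses post-scan, survival-dependent information. In the second case the modality hazard ratio is distorted whether or not FLT change is linked to it. With a link, the FLT hazard ratio is pushed towards or past 1, so a real association would tend to be understated.

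The direction was the same in every linked scenario run. The size cannot be derived from the documents: it depends on assumed survival, timing and frequency of later treatment, the strength of the link, and the direct FLT effect. The figures above are illustrations, not predictions for this trial. Because unaffected univariate models are also planned and the trial is an initial evaluation of 20 patients, this is a should-fix point.

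**What to change.** 1. In the Statistical Methodology row of the Study Summary, delete last treatment modality from the covariate list.
2. State there and in Section 9.3 (which has no covariate sentence, so one must be added) that the multiple Cox models adjust only for variables known by the interim scan, and that survival time in these models is counted from that scan. The PFS definition in 6.4.5, which starts at treatment, needs a cross-reference so that the two time origins are not confused.
3. If later treatment is of interest, add a labelled sensitivity analysis with resection and chemoradiation as time-dependent covariates that switch on at their start dates.

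The cost is a few sentences. Sample size, scans and patient care do not change. The adjusted model will no longer describe differences between later treatments, patients who progress before the interim scan leave the PFS model, and surgery and radiation dates must be taken from the chart if the sensitivity analysis is run.
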